11.0 Analysis Sets

11.1 Safety Analysis Set

The safety analysis set is defined as all subjects who received at least one dose of study drug in the considered period.

The main objective of the study is to characterize the safety of subjects with ADH1 treated with CLTX-305 (encaleret). All analyses of the safety and efficacy (PD) data will be performed using the safety analysis set.

- For Period 1, unless otherwise specified, all descriptive statistics will be presented by dose level and by day (and timepoint where applicable).
- For Period 2, unless otherwise specified, all descriptive statistics will be presented by day (and timepoint where applicable).
- For Period 3 and LTE, all descriptive statistics will be presented by period (and timepoint where applicable).

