### Secondary

# Periods 1 and 2:

Evaluate the effect of CLTX-305 (encaleret) to increase serum iPTH levels after both single and multiple doses across a dose range in participants with ADH1

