### Periods 1 and 2:

iPTH blood concentrations profiles (24-hours) over time after single and multiple doses of CLTX-305 (encaleret)

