### 6.1.2 Dosing and Administration

For details on Dosing of CLTX-305 (encaleret) see Section 8.2.

For additional background on Dose Justification see Section 4.3.

Dosing of CLTX-305 (encaleret) in participants with ADH1 is informed by prior experience of both acute and chronic dosing of CLTX-305 (encaleret) in the osteoporosis program that included exposures up to 1 year primarily in postmenopausal women with presumed normal CaSR function. The proposed starting dose is 30 mg in ADH1 because this is a dose proven to result in acute elevations in cCa in euparathyroid participants without an ADH1 mutations.

Based on peer-reviewed data from a pilot human study of a related calcilytic agent, NPSP795 (Roberts et al 2019), which also studied a top dose known to cause a rise in calcium in euparathyroid participants but not in ADH1 participants, we anticipate that the starting dose of 30 mg may be ineffective or minimally effective but represents a rational initial dose that has been demonstrated as safe and well tolerated previously.

Because a comprehensive safety database exists from the prior osteoporosis development program, including 12 months or more duration of safety exposure, the current first-in-ADH1 study will include repeat dosing, dose-escalation and dose individualization over time in individual ADH1 participants. Similar to cross-over designs, conducting dose-escalation within participants should reduce variability and increase the precision of dose/response modeling compared to an approach that might use separate parallel or sequential cohorts. Up to 16 participants studied should be feasible and allow characterization of individual and group mean dose-exposure-response profiles as well as proof-of-concept on elevation of cCa. Our approach is preferable since the ultra-orphan nature of the disease makes conventional parallel group dose finding not feasible.

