The first 7 participants who have completed CLTX-305-201 Period 2 and entered into Period 3 have had a wide range of CLTX-305 (encaleret) dose requirements from 10 mg once daily to 180 mg BID suggesting that CLTX-305 (encaleret) dosing is highly individualized. As a result, all remaining participants in Period 2 will receive an initial CLTX-305 (encaleret) 90 mg BID dose for at least 3-4 doses for evaluation of safety, tolerability and the ability to modulate cCa levels. The CLTX-305 (encaleret) dose will be up- or down-titrated as needed to maintain cCa levels below 10 mg/dL and blood phosphorus levels above the lower limit of normal. Dosing will be adjusted in 5, 10, 30, or 60 mg increments based on the available CLTX-305 (encaleret) tablet strengths. A frequent sampling test day with additional serial blood and urine sampling to assess 24-hour PK/PD profiles will be performed on Day 5. For details on the PK/PD timepoints during frequent sampling on Day 5 see Section 1.3.1 specifically Table J and Table K.

The total blood volume collected during Period 2 for Cohort 1 participants will be less than the blood volume limits per participant as per NIH Guidelines for Blood Draw Limits for Research Purposes (M95-9, June 2009). These volumes include the cumulative potential collection over an 8-week period: -10-14-day labs, Day -1 safety labs, Period 2 inpatient week, and 4 weeks of outpatient labs in Period 3. If a participant has a low body weight (<43 kg for adults or <48 kg for adolescents), the blood volume taken will be reduced to remain within the NIH guidelines of 10.5mL/kg/8w (adult) and 9.5 mL/kg/8w (pediatric). If, at any time, the CLTX-305 (encaleret) dose is associated with a cCa > 10 mg/dL, then the dose should be reduced to a lower dose level. An example of how CLTX-305 (encaleret) dosing may be adjusted is provided in Figure F below.

Figure F Dosing Guidance Algorithm for Period 2 – Cohort 1

BID= Two doses/day

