7.0 Study Objectives

This study is a single-site, open-label, dose-ranging study to evaluate the safety, tolerability and efficacy of CLTX-305 (encaleret) to maintain normalized albumin-corrected blood calcium (cCa) in subjects with hypocalcemia due to ADH1. The study consists of 2 cohorts, 3 periods and a Long-Term Extension (LTE) (Period 1, Period 2, Period 3 and Long-Term Extension [LTE]).

The **primary objectives** of this study are:

- Periods 1 and 2: Evaluate the safety and tolerability of single and multiple doses of CLTX-305 (encaleret) in subjects with ADH1.
- Period 3: Evaluate the safety, tolerability, and efficacy of CLTX-305 (encaleret) in subjects with ADH1 for 24 weeks.
- LTE: Evaluate the long-term (25 months or about 2 years) safety and tolerability of CLTX-305 (encaleret).

The **secondary objectives** of this study are:

Periods 1 and 2:

• Evaluate the effect of CLTX-305 (encaleret) to increase serum intact PTH (iPTH) levels after both single and multiple doses across a dose range in subjects with ADH1.

Periods 1, 2, and 3:

- Evaluate the PD effects of CLTX-305 on blood calcium concentrations.
- Evaluate the PD effects of CLTX-305 (encaleret) on associated measures of calcium. homeostasis including 1,25-(OH)₂ Vitamin D levels and urinary calcium excretion.
- Evaluate the PD effects of CLTX-305 (encaleret) on bone turnover markers including C-telopeptide (CTx) and procollagen type 1 N-propeptide (P1NP).
- Evaluate the PK of both single and multiple ascending doses of CLTX-305 (encaleret) in subjects with ADH1.

LTE:

- Obtain long-term data on efficacy to show durability of CLTX-305 (encaleret) on blood calcium concentrations.
- Evaluate the long-term PD effects of CLTX-305 (encaleret) on associated measures of mineral homeostasis including iPTH, 1,25-(OH)₂ Vitamin D levels and urinary calcium excretion.
- Evaluate the long-term effects of CLTX-305 on bone turnover markers including CTx and P1NP.

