13.8.2 Plasma Concentrations

Serum levels with below quantification level (BQL) results at the beginning of the profile (i.e. before the first measurable serum levels) are given a value of zero. BQL at end of profile (eg 48 hr) should be replaced with 1/2 LLOQ= 1 ng/mL). BLQ values embedded between two measurable values will be imputed as zero. For serum levels Above Level of Quantification (ALQ) the upper limit of quantification will be used.

Descriptive statistics (n, mean, SD, coefficient of variation % (%CV), median, minimum, maximum, geometric mean, and geometric CV) of PK concentration will be presented by period, visit, dose and timepoint for Period 1 and by period, visit, and timepoint for Period 2 and Period 3. Data listings of individual subject concentrations by time point, visit and period will be provided (unscheduled results will not be included in the listing).

In addition, the mean plasma concentrations and individual subject plasma concentrations will be presented in both the linear and semi-log scales by period, visit and timepoint.

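### The visible SAP has no within-participant dose-response summary of iPTH and cCa: Period 1 dose groups after Day 1 are selected by response, and Period 2 PD tables omit dose

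*SAP*

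**What the plan says.** **Purpose.** Protocol Section 3 and SAP 7.0 set a secondary objective for Periods 1 and 2: the effect of encaleret "to increase serum iPTH levels after both single and multiple doses across a dose range". The paired endpoint is "iPTH blood concentrations profiles (24-hours) over time after single and multiple doses of CLTX-305 (encaleret"), with no dose-response parameter or model named. Protocol 6.1.2 defends the design on the ground that "conducting dose-escalation within participants should reduce variability and increase the precision of dose/response modeling". Protocol 4.3 expects iPTH and cCa dose-response curves from Periods 1 and 2 that may inform PK-PD models.

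**Dosing.** Period 1 Day 1 is 30 mg for everyone (Protocol 6.1.3). Doses on Days 2 and 3 follow the participant's own maximum cCa (6.1.7, Figure E). The BID dose on Days 4 and 5 follows the participant's own cCa and/or iPTH (6.1.3, 8.2.1). There is no wash-out between doses. In Period 2 the remaining participants start at 90 mg BID and are then titrated (8.2.2).

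**Tables.** SAP 11.1 states "For Period 1, unless otherwise specified, all descriptive statistics will be presented by dose level and by day", then "For Period 2, unless otherwise specified, all descriptive statistics will be presented by day (and timepoint where applicable"). SAP 13.7.2 repeats this for the PD parameters, including iPTH and cCa: dose is a factor in Period 1 only. The Period 2 paired t-tests in SAP 13.7.4 pool all doses at each visit. Under SAP 13.8.2, PK concentrations are shown "by period, visit, and timepoint for Period 2 and Period 3", without dose. PK parameters differ: SAP 13.0 and 13.8.3 tabulate them by dose in Period 2 as well.

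**The concern.** In a titrated design the dose records how the participant has already responded. Sensitive participants are held at low doses and insensitive ones reach the top dose. A mean at each dose therefore mixes the drug effect with the kind of person who received that dose, and the two pull in opposite directions. The quantity free of this selection is the change within one participant from one dose to the next, which is what Protocol 6.1.2 invokes, yet no visible SAP section reports it for iPTH or cCa.

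What is at stake is the reading of the dose-ranging results. A table that appears to show a plateau or a fall at higher doses could be taken as pharmacology when it is selection. In Period 2 the PD tables have no dose axis.

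**Working it through.** There is no planned figure to reproduce. The sample size (approximately 16) has no power calculation behind it, and Protocol 9.1 plans no hypothesis testing. The check is a reading of the tabulation rules, a worked example and a simulation.

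**1. Which cells are selected by response?**
- Period 1 Day 1: no (fixed 30 mg).
- Period 1 Days 2-3: yes, through cCa.
- Period 1 Days 4-5: yes, through cCa and/or iPTH.
- Period 2 starting dose: no for those started at 90 mg BID; yes for earlier Cohort 1 participants, whose dose was individualised.
- Period 2 after titration: yes.

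**2. Is a within-participant dose summary planned?** SAP 13.7.1, 13.7.2 and 13.7.4 contain none. Individual profiles are planned for selected parameters by period, visit and timepoint, without dose. Listings will hold the raw data.

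**3. Worked example.** Assume cCa rises by 2 mg/dL per log10 of dose, the same for everyone, without noise. Take two participants one SD either side of a mean of 9.0 mg/dL at 30 mg, with SD 0.7: A at 9.70 and B at 8.30.
- A at 90 mg: 9.70 + 2 × log10(3) = 10.65. This exceeds 10.5, so Figure E gives 60 mg on Day 3: 9.70 + 2 × log10(2) = 10.30.
- B at 90 mg: 8.30 + 0.95 = 9.25. This is below 10.0, so Day 3 is 180 mg: 8.30 + 2 × log10(6) = 9.86.
- Across-dose slope on Day 3: (9.86 − 10.30) / log10(180/60) = −0.45 / 0.477 = −0.93 (unrounded cCa values).
- Within participants, Day 1 to Day 3: A 0.60 / 0.301 = 2.0; B 1.56 / 0.778 = 2.0.

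The by-dose table shows a fall; each participant shows the true rise.

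**4. Simulation of Period 1** (200,000 participants per scenario through Figure E). Assumptions, none from the documents: true slope 1 or 2 mg/dL per log10 dose; mean maximum cCa at 30 mg of 8, 9 or 10 mg/dL; between-participant SD 0.3, 0.7 or 1.2; noise SD 0.2; tolerability never limiting; parallel curves.

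| Slope estimated | True 1 | True 2 |
|---|---|---|
| Across dose, Day 2 | −3.62 to 0.28 | −2.60 to 1.28 |
| Across dose, Day 3 | −4.42 to 0.10 | −2.50 to 0.85 |
| Across dose, Days 1-3 pooled | −0.84 to 1.00 | −0.12 to 2.00 |
| Within participant | 1.00 to 1.11 | 2.00 to 2.13 |

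With true slope 2, mean 9 and SD 0.7, Day 3 mean cCa is 10.46 at 120 mg (about 2 of 8 participants) and 10.05 at 180 mg (about 4 of 8). With mean 8 and SD 0.3, practically everyone goes 30, 90, 180 mg and the pooled slope equals the truth: no selection, but dose and day coincide.

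**5. Limit of the within-participant estimate.** It removes selection, not the overlap of dose with day. With an assumed drift of −0.2 mg/dL per day it gives 1.49 to 1.68 for a true 2.

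**6. Period 2.** Assume a 90 mg BID start, mean cCa at that dose 8.5, 9.2 or 10 mg/dL, SD 1.0, lower limit 8.4 mg/dL, and dose halved or doubled from Day 3 with a 360 mg cap. With true slope 2 and mean 9.2, mean cCa is 9.20 on Day 1 and 9.18 on Day 5, so the by-day table carries no information on dose. Splitting Day 5 by dose gives slopes of −1.50 to −1.14 (true 1) and −0.93 to −0.62 (true 2): a dose column alone would mislead.

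**The case against.** The study is descriptive, and the endpoint paired with the objective is an iPTH profile, not a dose-response parameter. Period 1 is tabulated by dose and by day, and individual profiles and full listings will exist. That stands. A reader might infer that the objective cannot be answered at all; the documents do not support this, because a within-participant reading remains possible, though informal.

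A reader might want one figure for the loss. Take 400,000 simulated participants per scenario, baseline cCa 8.0 (SD 0.4), noise 0.2, and mean slopes of 0.55 to 0.9 mg/dL per natural-log unit with between-person SD 0.25 to 0.4. The true gain from 30 to 180 mg is 0.55 × ln 6 = 0.99 to 0.9 × ln 6 = 1.61 mg/dL. The by-dose table loses about 40% to 93% of it if the effect is assumed to start at 5 mg, but only about 0% to 4% if it starts at 30 mg. Protocol 4.3 and 6.1.2 expect 30 mg to be ineffective or minimally effective, so the high range is not one the documents support.

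All these figures concern cCa. iPTH is affected on Days 2 and 3 only so far as it tracks cCa, and directly on Days 4 and 5.

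A reader might also infer that each Period 2 table mixes a 36-fold dose range, from "dose requirements from 10 mg once daily to 180 mg BID" (360 / 10 = 36). Protocol 8.2.2 gives that as the requirements of the first 7 participants who completed Period 2 and entered Period 3, not the spread on a given Period 2 day. Nor is dose missing from all Period 2 output, since PK parameters are by dose.

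Finally, the Period 2 rule in SAP 11.1 allows exceptions, and SAP 10.13 (Period 2 special considerations) and 13.7.3 are missing from the copy reviewed. The explicit restriction in 13.7.2 makes an exception for the PD tables less likely, but does not rule one out.

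**Conclusion.** The point holds as a gap in the analysis plan. The visible SAP has no within-participant dose summary of iPTH or cCa, although the objective and the design rationale call for one. Raw Period 1 means by dose after Day 1 are not dose-response estimates. The bias runs from negligible, if nearly all participants stay below 10.0 mg/dL, to a reversed sign if they diverge in dose. The simulated sizes rest on an assumed log-linear cCa response and say nothing numerical about iPTH. Period 2 PD tables and Period 2-3 PK concentrations omit dose. No error rate or sample size is affected. This is an inexpensive improvement, subject to what SAP 10.13 and 13.7.3 contain.

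**What to change.** In SAP 13.7.2, for Periods 1 and 2:
- add the paired within-participant change in iPTH and cCa between successive actual doses, showing regimen (QD or BID) and study day;
- label the individual profiles with the actual dose;
- state that raw across-dose means after Period 1 Day 1 are not dose-response estimates, and that dose and day overlap because there is no wash-out.

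In SAP 13.8.2, show Period 2-3 PK concentrations by dose or dose-normalised.

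Do not add a Period 2 by-dose PD table without the within-participant summary beside it, since alone it repeats the selection problem. A mixed model is optional.

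The cost is SAP wording and a few outputs from data already collected; dosing and sample size do not change. With up to 8 participants in Period 1 the estimates will be imprecise.

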11.2 PK Analysis Set

The PK analysis set is defined as all subjects who received at least one dose of study drug and who have at least one non-missing PK concentration results.

12.0 Reporting Analyses

Due to the open-label study design and quantitative laboratory analytes used to derive PK and PD endpoints, both Sponsor and investigator will be able to conduct joint periodic data reviews on an ongoing basis throughout the study.

Review of safety, tolerability and effects on iPTH and cCa will be conducted on Period 1 single-dose and multiple-dose (QD and BID) responses prior to commencement of Cohort 2.

Review of safety, tolerability and effects on selected PD endpoints will be conducted on all data collected by the time the last subjects has completed Period 2.

No formal interim analysis will be done.

A CSR will be written at the end of the Period 3. The Period 3 CSR will include all the data collected in Period 1, Period 2 and Period 3. An addendum to the CSR will be written to report the LTE data.

13.0 Statistical Methods

All data collected during this study will be displayed in data listings. Data listings will be sorted by period, cohort, and subject identifier. In addition, listings will include all relevant derived variables. The summary tables will be presented for by period, and by visit and timepoint when relevant.

Demographic and baseline summaries will be presented for each period; periods may be combined if the same subjects are included (and the data summarized is the same). Unless otherwise noted, categorical variables will be summarized using counts and percentages. Percentages will be rounded to one decimal place, except 100% will be displayed without any decimal places and percentages will not be displayed for zero counts.

Continuous variables will be summarized using the number of observations (n), mean, standard deviation (SD), median, minimum and maximum. The first and third quartile estimates (Q1 and Q3) will additionally be reported in descriptive analyses of continuous variables.

Summary statistics will be tabulated for each of the PK parameters by dose level and by study day separately for Period 1 and Period 2. Geometric means and coefficients of variation will be presented for C_{max} , C_{trough} , AUC_{0-t} , AUC_{0-24} , AUC_{0-inf} , AUC_{0-tau} , and $T_{1/2}$. Median, minimum and maximum will be presented for T_{max} . Actual times will be used for PK parameter reporting unless they are not available. In such cases nominal times will be used.

The mean, median, Q1 and Q3 values will be displayed with 1 decimal place, the minimum and maximum will be displayed with 0 or 1 decimal place depending on the data and the SD will be displayed with two additional decimal places. For fractional calcium excretion, the mean, median, minimum, maximum, Q1, Q3 and SD values will be displayed with 3 decimal places.

No formal statistical tests will be performed on efficacy variables; however, post-hoc inferential statistics will be carried out for specific parameters. Statistical hypothesis testing will be 2-tailed and carried out at the 5% level of significance.

All analyses will use SAS version 9.4 or higher.

This is a single site study. No subgroup analyses will be performed. No adjustments for multiplicity will be made.

13.1 Subject Disposition

The number and percentage of subjects treated in the study will be presented by Period. Disposition will be summarized for each period with the number and percentage of subjects who completed the treatment for each period, who withdrew from the treatment, withdrew from the study prematurely with a breakdown of the corresponding reasons for withdrawal.

The subject disposition summary will include:

- Number (%) of subjects in the safety analysis set,
- Number (%) of subjects who completed each period,
- Number (%) of subjects who prematurely discontinued from the study.

13.2 Important Protocol Deviations

It is the responsibility of the investigator to use continuous vigilance to identify and report deviations to the NIH Institutional Review Board (IRB) as per Policy 801. Deviations will be identified, listed, coded and summarized by the Sponsor/ designee (Clinical Research Organization [CRO]) and must be addressed in study source documents and reported to the Sponsor/designee CRO. The investigator is responsible for knowing and adhering to the reviewing IRB requirements. Additional details on the process and procedures of identifying and managing protocol deviations will be available in the Sponsor/designee (CRO) data monitoring plan.

Per CRO processes, important protocol deviations data will be entered into CRO system of record Predictivv Study Operations (PSO). The CRO study team and the Sponsor will conduct on-going reviews of the deviation data from PSO.

Additional listings to aid the Sponsor and CRO in the review of data and identification of possible deviations may be programmed if required. These additional listings will not form part of the Table, Figure and Listing (TFL) deliverable.

Important protocol deviations (IPD) are a subset of protocol deviations that might significantly affect the completeness, accuracy, and/or reliability of the study data or that might significantly affect a subject's rights, safety, or well-being. The sponsor and study team will review and categorize IPDs.

IPDs will be summarized by category and by Period and Overall for the Safety Analysis Set. A list of subjects with IPDs will be presented by Period.

13.2.1 NIH Definition of Protocol Deviation

A protocol deviation is any changes, divergence, or departure from the IRB-approved research protocol.

- Major deviations: Deviations from the IRB approved protocol that have, or may have the potential to, negatively impact the rights, welfare or safety of the subject, or to substantially negatively impact the scientific integrity or validity of the study.
- Minor deviations: Deviations that do not have the potential to negatively impact the rights, safety or welfare of subjects or others, or the scientific integrity or validity of the study.

13.3 Treatments

13.3.1 Extent of Study Drug Exposure

Exposure data will be summarized for Period 3 and LTE only using the Safety Analysis Set. The average daily dose for each period will be summarized for each period. The average daily dose will be derived as the sum of the dose levels times the number of days on each dose, divided by the number of days in the period considered. Additionally, the number of missed doses by period will be summarized.

13.3.2 Concomitant Medications

Medications received either prior to or concomitantly with study drug will be categorized by Anatomical Therapeutic Chemical Classification (ATC) and preferred name (PN) according to World Health Organization (WHO) Drug dictionary (version 2021MAR01 Global B3 or later). Prior and concomitant medications will be included in a subject data listing, and tabulated separately for Period 1 and for all subjects in the Safety Analysis Set. The prior and concomitant medication tables will be sorted by descending frequency in the medication class, followed by descending frequency PN.

